## 6.9.4. Premature Study Discontinuation

A primary goal of this study is to assess the safety of a combination of products in participants with CHB. Therefore, every effort should be made to retain participants on study to assess safety outcomes. Participants who stop study treatments must therefore be maintained on study and continue study evaluations.

If this is not possible or acceptable to the participant or investigator, the participant may be withdrawn from the study and an early study discontinuation visit should be performed. The early study discontinuation visit should be performed within 14 days from determination by participant or investigator of study discontinuation.

Other reasons for study discontinuation:

- Request by participant to withdraw from study
- Request by study investigator or participant's primary physician/provider

The following assessments will be performed at the study discontinuation visit:

- Perform complete physical examination
- Ophthalmologic examination and chest x-ray, as needed
- Collect vital signs and body weight

- 12-lead ECG (Participant must rest quietly in the supine position for a minimum of 5 minutes prior to the recording)
- Review AEs and concomitant medications
- Obtain blood samples for laboratory assessments as follows:
  - Safety laboratory tests (hematology and chemistry and coagulation)
  - Urinalysis
  - Qualitative and quantitative HBV serology (HBsAg, HBcrAg, HBeAg, and HBV RNA)
  - Quantitative plasma HBV DNA
  - Serum sample for HBV viral sequencing
  - Serum pregnancy test (females of childbearing potential only)
  - Estimated CLcr (using Cockcroft-Gault method)
  - APRI and FibroTest
  - TSH

## 6.10. End of Study

The end of this study will be last participant's last observation.

## 6.11. Poststudy Care

Once a participant has completed their study participation, the long-term care of the participant will return to the responsibility of their primary treating physicians.

## 6.12. Sample Storage

The stored biological samples may be used by Gilead or its research partner for future testing to provide additional data to answer questions that relate to the main study. At the end of this study, these samples may be retained in storage by Gilead for a period up to 15 years.

## 7. ADVERSE EVENTS AND TOXICITY MANAGEMENT

#### 7.1. Definitions of Adverse Events and Serious Adverse Events

#### 7.1.1. Adverse Events

An AE is any untoward medical occurrence in a clinical study participant administered a study drug, which does not necessarily have a causal relationship with the treatment. An AE can therefore be any unfavorable and/or unintended sign, symptom, or disease temporally associated with the use of a study drug, whether or not the AE is considered related to the study drug. Adverse events may also include pretreatment or posttreatment complications that occur as a result of protocol-specified procedures or special situations (Section 7.1.3).

An AE does not include the following:

- Medical or surgical procedures such as surgery, endoscopy, tooth extraction, and transfusion. The condition that led to the procedure may be an AE and must be reported.
- Preexisting diseases, conditions, or laboratory abnormalities present or detected before the screening visit that do not worsen.
- Situations where an untoward medical occurrence has not occurred (eg, hospitalization for elective surgery, social and/or convenience admissions).
- Overdose without clinical sequelae (Section 7.1.3).
- Any medical condition or clinically significant laboratory abnormality with an onset date before the ICF is signed and not related to a protocol-associated procedure is not an AE but rather considered to be preexisting and should be documented as medical history.

Preexisting events that increase in severity or change in nature after study drug initiation or during or as a consequence of participation in the clinical study will also be considered AEs.

#### 7.1.2. Serious Adverse Events

An SAE is defined as an event that, at any dose, results in the following:

- Death
- A life-threatening situation (Note: The term "life-threatening" in the definition of "serious" refers to an event in which the participant was at risk of death at the time of the event; it does not refer to an event that hypothetically might have caused death if it were more severe.)
- In-patient hospitalization or prolongation of existing hospitalization

- Persistent or significant disability/incapacity
- A congenital anomaly/birth defect
- A medically important event or reaction: Such events may not be immediately life-threatening or result in death or hospitalization but may jeopardize the participant or may require intervention to prevent one of the other outcomes constituting SAEs. Medical and scientific judgment must be exercised to determine whether such an event is reportable under expedited reporting rules. Examples of medically important events include intensive treatment in an emergency room or at home for allergic bronchospasm; blood dyscrasias or convulsions that do not result in hospitalization; and development of drug dependency or drug abuse.

## 7.1.3. Study Drugs and Gilead Concomitant Therapy Special Situations Reports

Special situation reports (SSRs) include all reports of medication error, abuse, misuse, overdose, occupational exposure, drug interactions, exposure via breastfeeding, unexpected benefit, transmission of infectious agents via the product, counterfeit of falsified medicine, and pregnancy regardless of an associated AE.

Medication error is any unintentional error in the prescribing, dispensing, preparation for administration or administration of a study drug while the medication is in the control of a health care professional, patient, or consumer. Medication errors may be classified as a medication error without an AE, which includes situations of missed dose, medication error with an AE, intercepted medication error, or potential medication error.

Abuse is defined as persistent or sporadic intentional excessive use of a study drug by a participant.

Misuse is defined as any intentional and inappropriate use of a study drug that is not in accordance with the protocol instructions or the local prescribing information.

An overdose is defined as an accidental or intentional administration of a quantity of a study drug given per administration or cumulatively which is above the maximum recommended dose as per protocol or in the product labeling (as it applies to the daily dose of the participant in question). In cases of a discrepancy in drug accountability, overdose will be established only when it is clear that the participant has taken the excess dose(s). Overdose cannot be established when the participant cannot account for the discrepancy, except in cases in which the investigator has reason to suspect that the participant has taken the additional dose(s).

Occupational exposure is defined as exposure to a study drug as a result of one's professional or nonprofessional occupation.

Drug interaction is defined as any drug/drug, drug/food, or drug/device interaction.

Unexpected benefit is defined as an unintended therapeutic effect where the results are judged to be desirable and beneficial.

Transmission of infectious agents is defined as any suspected transmission of an infected agent through a Gilead study drug.

Counterfeit or falsified medicine: Any study drug with a false representation of (a) its identity, (b) its source, or (c) its history.

#### 7.2. Assessment of Adverse Events and Serious Adverse Events

The investigator or qualified subinvestigator is responsible for assessing AEs and SAEs for causality and severity, and for final review and confirmation of accuracy of event information and assessments.

## 7.2.1. Assessment of Causality for Study Drugs and Procedures

The investigator or qualified subinvestigator is responsible for assessing the relationship to study drug using clinical judgment and the following considerations:

- No: Evidence exists that the AE has an etiology other than the study drug. For SAEs, an alternative causality must be provided (eg, preexisting condition, underlying disease, intercurrent illness, concomitant medication).
- Yes: There is reasonable possibility that the AE may have been caused by the study drug.

It should be emphasized that ineffective treatment should not be considered as causally related in the context of AE reporting.

The relationship to study procedures (eg, invasive procedures such as venipuncture or biopsy) should be assessed using the following considerations:

- No: Evidence exists that the AE has an etiology other than the study procedure.
- Yes: The AE occurred as a result of protocol procedures (eg., venipuncture).

## 7.2.2. Assessment of Severity

The severity of AEs will be graded using the Gilead Sciences Inc. (GSI) Toxicity Grading Scale, Version 01 April 2015, with the exception of IRRs. For each episode, the highest grade attained should be reported as defined in the Toxicity Grading Scale (Appendix 11.5).

Grading of IRRs will be done according to the Common Terminology Criteria for Adverse Events (CTCAE) Version 5.0 found on the National Cancer Institute (NCI) website:

 $https://ctep.cancer.gov/protocoldevelopment/electronic\_applications/docs/CTCAE\_v5\_Quick\_R\\ eference\_5x7.pdf$ 

## 7.3. Investigator Reporting Requirements and Instructions

## 7.3.1. Requirements for Collection Prior to Study Drug Initiation

After informed consent, but prior to initiation of study medication, the following types of events must be reported on the applicable eCRFs: all SAEs and AEs related to protocol-mandated procedures.

#### 7.3.2. Adverse Events

Following initiation of study medication, collect all AEs, regardless of cause or relationship, until the end of the study including the posttreatment FU visit and report them on the eCRFs as instructed.

All AEs should be followed until resolution or until the AE is stable, if possible. Gilead may request that certain AEs be followed beyond the protocol-defined FU period.

#### 7.3.3. Serious Adverse Events

All SAEs, including deaths regardless of cause or relationship, that occur after the participant first consents to participate in the study (ie, signing the ICF) and throughout the duration of the study, including the posttreatment FU visit, must be reported on the applicable eCRFs and to Patient Safety (PS, formerly Global Patient Safety) as instructed below in this section. This also includes any SAEs resulting from protocol-associated procedures performed after the ICF is signed.

Investigators are not obligated to actively seek SAEs after the protocol-defined FU period; however, if the investigator learns of any SAEs that occur after the protocol-defined FU period has concluded and the event is deemed relevant to the use of study drug, the investigator should promptly document and report the event to Gilead PS.

Instructions for reporting SAEs are described in Section 7.4.1.

## 7.3.4. Study Drug Special Situations Reports

All study drug SSRs that occur from study drug initiation and throughout the duration of the study, including the posttreatment FU visit, must be reported to Gilead PS (Section 7.4.2). Adverse events and SAEs resulting from SSRs must be reported in accordance to the AE and SAE reporting guidance (Section 7.3).

## 7.3.5. Concomitant Therapy Reports

## 7.3.5.1. Gilead Concomitant Therapy Special Situations Report

Special situation reports involving a Gilead concomitant therapy (not considered study drug), that occurs after the participant first consents to participate in the study (ie, signing the ICF) and

throughout the duration of the study, including the posttreatment FU visit, must be reported to Gilead PS utilizing the paper SSR (Section 7.4.2.2).

## 7.3.5.2. Non-Gilead Concomitant Therapy Report

Special situations involving non-Gilead concomitant medications does not need to be reported on the SSR form; however, for special situations that result in AEs due to a non-Gilead concomitant medication, the AE should be reported on the AE form.

Any inappropriate use of concomitant medications prohibited by this protocol should not be reported as "misuse," but may be more appropriately documented as a protocol deviation.

All clinical sequelae in relation to these SSRs will be reported as AEs or SAEs at the same time using the AE eCRF and/or the SAE report form. Details of the symptoms and signs, clinical management, and outcome will be reported, when available.

## 7.4. Reporting Process for Serious Adverse Events and Special Situation Reports

## 7.4.1. Serious Adverse Event Reporting Process

- For fatal or life-threatening events, copies of hospital case reports, autopsy reports, and other
  documents are also to be transmitted by email or fax when requested and applicable.
   Transmission of such documents should occur without personal participant identification,
  maintaining the traceability of a document to the participant identifiers.
- Additional information may be requested to ensure the timely completion of accurate safety reports.
- Any medications necessary for treatment of the SAE must be recorded onto the concomitant medication section of the participant's eCRF and the SAE narrative section of the Safety Report Form eCRF.

## 7.4.1.1. Electronic Serious Adverse Event Reporting Process

• Site personnel will record all SAE data on the applicable eCRFs and from there transmit the SAE information to Gilead PS within 24 hours of the investigator's knowledge of the event from ICF signature throughout the duration of the study, including the protocol-required posttreatment FU period. Detailed instructions can be found in the eCRF completion guidelines.

• If for any reason it is not possible to record and transmit the SAE information electronically, record the SAE on the paper SAE reporting form and transmit within 24 hours to:

Gilead PS

Email: Safety [contact]

or

[contact]

- As soon as it is possible to do so, any SAE reported via paper must be transcribed on the applicable eCRFs according to instructions and within the timelines outlined in the eCRF completion guidelines.
- If an SAE has been reported via a paper form because the eCRF database has been locked, no further action is necessary. If the database is not locked, any SAE reported via paper must be transcribed as soon as possible on the applicable eCRFs and transmitted to PS.
- For fatal or life-threatening events, copies of hospital case reports, autopsy reports, and other
  documents are also to be submitted by email or fax when requested and applicable.
   Transmission of such documents should occur without personal participant identification,
  maintaining the traceability of a document to the participant identifiers.
- Additional information may be requested to ensure the timely completion of accurate safety reports.
- Any medications necessary for treatment of the SAE must be recorded onto the concomitant medication section of the participant's eCRF and the SAE narrative section of the Safety Report Form eCRF.

## 7.4.2. Special Situations Reporting Process

#### 7.4.2.1. Paper Special Situations Reporting Process for Study Drug

 All SSRs will be recorded on the SSR form and transmitted by emailing or faxing the report form within 24 hours of the investigator's knowledge of the event to the attention of Gilead PS from study drug initiation throughout the duration of the study, including the protocol-required posttreatment FU period.

Gilead PS

Email: Safety [contact]

or

[contact]

## 7.4.2.2. Reporting Process for Gilead Concomitant Medications

• Special situations that involve Gilead concomitant medications that are not considered study drug must be reported within 24 hours of the investigator's knowledge of the event to Gilead PS utilizing the paper SSR form to:

Gilead PS

Email: Safety [contact]

or

[contact]

- Any inappropriate use of concomitant medications prohibited by this protocol should not be reported as "misuse," but may be more appropriately documented as a protocol deviation.
- Special situations involving non-Gilead concomitant medications do not need to be reported on the SSR form; however, special situations that result in AEs due to a non-Gilead concomitant medication, must be reported as an AE.

## 7.4.2.3. Pregnancy Reporting Process

• The investigator should report pregnancies in female study participants and/or female partners of male participants who are identified after initiation of study drug and throughout the study, including the posttreatment FU period, to Gilead PS using the pregnancy report form within 24 hours of becoming aware of the pregnancy. Contact details for transmitting the pregnancy report form are as follows:

Gilead PS

Email: Safety [contact]

or

[contact]

- The pregnancy itself is not considered an AE, nor is an induced elective abortion to terminate a pregnancy without medical reasons.
- All other premature terminations of pregnancy (eg, a spontaneous abortion, an induced therapeutic abortion due to complications or other medical reasons) must be reported within 24 hours as an SAE, as described in Section 7.4.1. The underlying medical reason for this procedure should be recorded as the AE term.
- A spontaneous abortion is always considered to be an SAE and will be reported as described in Section 7.4.1. Furthermore, any SAE occurring as an adverse pregnancy outcome after study completion must be reported to the Gilead PS.
- The participant should receive appropriate monitoring and care until the conclusion of the pregnancy. The outcome of the pregnancy/partner pregnancy should be reported to Gilead PS using the pregnancy outcome report form. If the end of the pregnancy/partner pregnancy

occurs after the study has been completed, the outcome should be reported directly to Gilead PS. Gilead PS contact information is as follows: email: Safety\[contact] and [contact].

• Refer to Appendix 11.4 for Pregnancy Precautions, Definition for Female of Childbearing Potential, and Contraceptive Requirements.

## 7.5. Gilead Reporting Requirements

Depending on relevant local legislation or regulations, including the applicable US FDA CFR, the EU Clinical Trials Directive (2001/20/EC) and relevant updates, and other country-specific legislation or regulations, Gilead may be required to expedite to worldwide regulatory agencies reports of SAEs, which may be in the form of line listings, serious adverse drug reactions (SADRs), or suspected unexpected serious adverse reactions (SUSARs). In accordance with the EU Clinical Trials Directive (2001/20/EC), Gilead or a specified designee will notify worldwide regulatory agencies and the relevant IEC in concerned Member States of applicable SUSARs as outlined in current regulations.

Assessment of expectedness for SAEs will be determined by Gilead using reference safety information specified in the IB or relevant local label as applicable.

All investigators will receive either a safety letter or quarterly SUSAR line listing (applicable for United Kingdom and European Economic Area sites) notifying them of relevant SUSAR reports associated with any study drug. The investigator should notify the IRB or IEC of SUSAR reports as soon as is practical, where this is required by local regulatory agencies, and in accordance with the local institutional policy.

## 7.6. Clinical Laboratory Abnormalities and Other Abnormal Assessments as Adverse Events or Serious Adverse Events

Laboratory abnormalities without clinical significance are not to be recorded as AEs or SAEs. However, laboratory abnormalities (eg, clinical chemistry, hematology, urinalysis) that require medical or surgical intervention or lead to study drug interruption, modification, or discontinuation must be recorded as an AE, as well as an SAE, if applicable. In addition, laboratory or other abnormal assessments (eg, ECG, x-rays, vital signs) that are associated with signs and/or symptoms must be recorded as an AE or SAE if they meet the definition of an AE or SAE as described in Sections 7.1.1 and 7.1.2. If the laboratory abnormality is part of a syndrome, record the syndrome or diagnosis (eg, anemia), not the laboratory result (ie, decreased hemoglobin).

Severity should be recorded and graded according to the GSI Grading Scale (see reference table in Appendix 11.5: Toxicity Grading Scale, Version 01 April 2015). For AEs associated with laboratory abnormalities, the event should be graded on the basis of the clinical severity in the context of the underlying conditions; this may or may not be in agreement with the grading of the laboratory abnormality.

## 7.7. Toxicity Management

All clinical and clinically significant laboratory toxicities will be managed according to uniform guidelines detailed in Appendix 11.6.

- Grade 3 and 4 clinically significant laboratory abnormalities should be confirmed by repeat testing within 3 calendar days of receipt of results and before study drug discontinuation, unless such a delay is not consistent with good medical practice
- Clinical events and clinically significant laboratory abnormalities will be graded according to the Table for GSI Grading Scale for Severity of Adverse Events and Laboratory Abnormalities (Appendix 11.5)
- When restarting study drug following resolution of the AE, the study drug should be restarted at full dose or modified dose that is dependent upon discussion with the medical monitor
- Any recurrence of the study drug—related Grade 3 or 4 clinical or clinically significant laboratory AE following dose interruption mandates permanent discontinuation of study drug
- Administration of study drug(s) may be discontinued due to a clinical or laboratory event.
   The medical monitor should be consulted prior to dose discontinuation of study drug(s) unless the investigator believes that immediate action is warranted to ensure the continued safety of the participant
- Any questions regarding toxicity management should be directed to the medical monitor.

## 7.7.1. Grades 1 and 2 Laboratory Abnormality or Clinical Event

Continue study drug at the discretion of the investigator.

## 7.7.2. Grade 3 Laboratory Abnormality or Clinical Event

- For Grade 3 laboratory abnormality or clinical event, study drug may be continued if the event is considered to be unrelated to study drug
- For any study drug-related, Grade 3 AE, study drug should be held
- For any study drug—related ≥ Grade 3 AE not able to be medically managed (eg, nausea with antiemetics), study drug should be permanently discontinued
- For a confirmed laboratory abnormality, study drug—related Grade 3, study drug would be held until toxicity returns to ≤ Grade 2. If a laboratory abnormality recurs to ≥ Grade 3 following rechallenge, study drug should be permanently discontinued, and the participant managed according to local practice. Recurrence of laboratory abnormalities considered unrelated to study drug may not require permanent discontinuation.

• For a Grade 3 clinical event, or clinically significant laboratory abnormality confirmed by repeat testing within 3 calendar days that is considered to be related to study drug, study drug should be withheld until the toxicity returns to ≤ Grade 2

## 7.7.3. Grade 4 Laboratory Abnormality or Clinical Event

- For a Grade 4 clinical event or clinically significant Grade 4 laboratory abnormality confirmed by repeat testing within 3 calendar days, the study drug should be permanently discontinued, and the participant managed according to local practice. The participant should be followed as clinically indicated until the laboratory abnormality returns to Day 1 of treatment or is otherwise explained, whichever occurs first. A clinically significant Grade 4 laboratory abnormality that is not confirmed by repeat testing should be managed according to the algorithm for the new toxicity grade.
- A Grade 4 laboratory abnormality or clinical event that is not considered clinically significant by the investigator may also be tested for confirmation and study drug continued at the discretion of the investigator.
- The study drug may be continued without dose interruption for a clinically nonsignificant Grade 4 laboratory abnormality (eg, Grade 4 CK after strenuous exercise or triglyceride elevation that is nonfasting or that can be medically managed).

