### 5.5. Accountability for Investigational Medicinal Product: SLGN, TAF, VIR-2218, and Nivolumab

The investigator is responsible for ensuring adequate accountability of all used and unused study drug. This includes acknowledgment of receipt of each shipment of study drug (quantity and condition). All used and unused study drug dispensed to participants must be returned to the site.

Each study site must keep accountability records that capture:

- The date received and quantity of study drug
- The date, participant number, and the study drug kit number dispensed
- The date, quantity of used and unused study drug returned, along with the initials of the person recording the information

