## 6.9. Assessments for Early Discontinuation of Study Treatment

## 6.9.1. Criteria for Discontinuation of Study Treatment

Study treatment(s) that are considered related by the investigator to any of the below event(s) will be held in a participant until resolution of the event:

- Any study drug-related AE  $\geq$  Grade 3
- A confirmed, clinically significant laboratory test abnormality (other than ALT) ≥ Grade 3 considered study drug(s) related by the investigator

Study treatment(s) may be reinitiated following resolution of the above event(s) after discussion with the medical monitor. Study treatment(s) should be restarted in line with their preassigned schedules.

Study treatment(s) that are considered related by the investigator to any of the below events will be permanently discontinued:

- Any on-treatment uveitis, confirmed by ophthalmologic evaluation
- Any confirmed recurrence of study drug—related Grade 3 or 4 (excluding laboratory abnormalities) AE following dose interruption mandates permanent discontinuation of study drug(s)
- Unacceptable toxicity or toxicity that, in the judgment of the investigator, compromises the ability to continue study-specific procedures or is considered not to be in the participant's best interest
- Any study drug-related Grade 4 AE (excluding laboratory abnormalities)
- Any study drug—related ≥ Grade 3 AE not able to be medically managed (eg, nausea with antiemetics)
- Any confirmed study drug-related laboratory abnormality  $\geq$  Grade 3 following rechallenge
- A clinically significant Grade 4 laboratory abnormality
- Virological breakthrough: as defined in Section 2

Additional criteria for permanent discontinuation of study treatment(s):

- Intercurrent illness that would, in the judgment of the investigator, affect assessments of clinical status to a significant degree
- Hepatic disease progression or lack of efficacy defined as participants in Cohorts 1 and 2 (Group A) who do not achieve HBsAg decline ≥ 0.2 log10 IU/mL at Week 12
- Participant requests to discontinue for any reason
- Participant noncompliance
- Pregnancy during the study
- At the discretion of the investigator, Gilead, a regulatory agency or an institutional review board (IRB), or independent ethics committee (IEC).

If a participant discontinues study dosing (eg, as a result of an AE), every attempt should be made to keep the participant in the study and continue to perform the required study-related FU and procedures.

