Persistent ALT > 2 × baseline and $\geq$ 5 × ULN without evidence of hepatic toxicity, as defined below	Continue study treatment(s), ALT should be evaluated every 2 weeks or more frequently as clinically needed, until ALT < 5 × ULN
Confirmed ALT > 2 × nadir, with evidence of hepatic toxicity, defined as any one of the following confirmed laboratory abnormalities:  Total bilirubin > 2 × ULN  Elevated INR > 0.5 above baseline AND > ULN  Abnormal serum albumin > 1 g/dL decrease from baseline	Cohort 1: Permanently discontinue study treatment(s) except TAF 25 mg once daily. Participant should be monitored weekly until ALT < 5 × ULN, and total bilirubin, INR, and albumin values return to normal or baseline levels.  Cohort 2: Initiate commercially approved NUC treatment once daily and permanently discontinue study treatment(s). Participant should be monitored weekly until ALT < 5 × ULN, and total bilirubin, albumin, and/or INR values return to normal or baseline levels

ALT = alanine aminotransferase; INR = international normalized ratio; NUC = nucleos(t)ide(s); SLGN = selgantolimod; TAF = tenofovir alafenamide; ULN = upper limit of normal

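### Section 7.7.3 lets study drug continue after a drug-related Grade 4 clinical event that Section 6.9.1 and the synopsis say must stop it, and does not name the drug to be stopped

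*Supplement*

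**What the plan says.** Section 6.9.1 opens its list of permanent stops with "Study treatment(s) that are considered related by the investigator to any of the below events will be permanently discontinued". One listed trigger is "Any study drug-related Grade 4 AE (excluding laboratory abnormalities"). The synopsis carries the same item under the same lead-in. In both lists clinical significance qualifies only the separate Grade 4 laboratory item.

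Section 7.7.3 gives its own Grade 4 instructions:

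- The first bullet begins "For a Grade 4 clinical event or clinically significant Grade 4 laboratory abnormality" and, after a requirement for repeat testing, says "the study drug should be permanently discontinued, and the participant managed according to local practice". It sets no relatedness condition and does not say which drug.
- The second bullet covers "A Grade 4 laboratory abnormality or clinical event that is not considered clinically significant by the investigator". It permits confirmatory testing and continued study drug at the investigator's discretion, again with no relatedness condition.
- The third bullet permits continuation for clinically nonsignificant Grade 4 laboratory findings, with creatine kinase and triglycerides as examples.

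TAF counts among the study drugs. Section 5.5 is headed "Accountability for Investigational Medicinal Product: SLGN, TAF, VIR-2218, and Nivolumab", and Section 6.6 includes oral TAF under study drug administration. For ALT elevation with hepatic toxicity in Cohort 1, Table 6 in Section 7.7.5 instructs "Permanently discontinue study treatment(s) except TAF 25 mg once daily".

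**The concern.** These are operative stopping rules in a study whose first primary objective is safety and tolerability. Section 1.5 describes the risk of the three-agent combination as unknown. A site that follows the second bullet of 7.7.3 could keep dosing a participant whose related treatment 6.9.1 says must end.

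The first bullet raises a different problem. A site that takes it at face value could withdraw TAF from a participant who needs viral suppression, after an event that has nothing to do with TAF.

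Reporting is touched as well. Section 8.6.2 makes any adverse event leading to premature discontinuation of a study drug a treatment-emergent event and summarises such events separately. Which section a site follows can therefore alter that count.

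**Working it through.** The plan gives no figure to reproduce, so the check sets the rules side by side for a Grade 4 clinical event.

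| Event | Section 6.9.1 and synopsis | Section 7.7.3 | Result |
|---|---|---|---|
| Related, clinically significant | Related treatment(s) must stop | Unnamed study drug should stop | Same direction; 7.7.3 does not identify the drug |
| Related, judged not clinically significant | Related treatment(s) must stop; no exception | Second bullet: may continue | Contradiction |
| Unrelated, clinically significant | No Grade 4 stop; discretionary stops available | First bullet: should stop | Different rules, but both can be followed |
| Unrelated, judged not clinically significant | No Grade 4 stop; discretionary stops available | First bullet read literally: should stop; second bullet: may continue | Tension within 7.7.3 |

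**The contradiction.** It lies in the second row. An investigator who continues drug there complies with 7.7.3 and breaches 6.9.1. The second bullet is also out of step with the Grade 3 rules: 6.9.1 and 7.7.2 both hold drug for a related Grade 3 event, so the second bullet is more permissive for a related Grade 4 event than the neighbouring text is for a related Grade 3 one.

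**Can the second row occur?** Most clinical Grade 4 definitions in Appendix 11.5 describe life-threatening or disabling events, which an investigator would hardly call insignificant. A few do not. Fever above 40.5 °C is Grade 4 on the number alone, and headache is Grade 4 if hospitalization is indicated. Section 1.5 lists pyrexia and headache among related events with VIR-2218, though at Grade 1 or 2. The row is small but not empty.

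**Does another text settle it?** Section 3.6 refers the reader to 6.9 for discontinuation criteria. Section 1.5 cites 6.9.1 for the parameters leading to modification, interruption or discontinuation, and cites 7.7.4 only for immune-related events. Section 6.9.2 sends the reader to 7.7 for ALT elevations only. The text shown of Appendix 11.6 covers nivolumab-related events only. Together these favour 6.9.1 as the governing text, but none says that it overrides 7.7.3.

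**Which drug does the first bullet stop?** Sections 5.5 and 6.6 make TAF a study drug. Elsewhere the protocol separates it: Table 6 exempts it by name in Cohort 1, and the pregnancy procedure in Appendix 11.4 names nivolumab, selgantolimod and VIR-2218 and leaves other drugs for discussion. Section 7.7.3 makes no such distinction. The participants concerned are those in Cohort 1, plus any in Cohort 2 who were started on TAF for ALT of at least 10 × ULN under Table 6. No fixed number can therefore be put on them.

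**Scale of one case.** With a planned 40 participants in Cohort 1 and 40 in Cohort 2 Group A, one participant handled differently moves that group's discontinuation percentage by 1/40 = 2.5 points. This is not a forecast that a case will occur.

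**The case against.** The best defence has four parts.

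1. **6.9.1 governs.** The cross-references in Sections 3.6 and 1.5, and the matching synopsis, point that way. This stands as evidence of intent, so a reader should not infer that the protocol is silent on where discontinuation criteria belong. It does not remove a conflicting instruction from the section that an investigator would open when managing toxicity.

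2. **The second bullet is really about laboratory results.** Testing for confirmation fits laboratory values, and the third bullet's examples are all laboratory ones. This is probably right. It supports reading *or clinical event* as a drafting slip, and so supports deleting it.

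3. **The unrelated-event difference is no contradiction.** A reader might infer that 7.7.3 and 6.9.1 are irreconcilable for unrelated Grade 4 events. The documents do not support that. Section 6.9.1 allows stops for intercurrent illness and at the investigator's discretion, so a site that stops drug complies with both. This objection stands in full.

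4. **Safeguards exist.** Section 7.7 sends questions to the medical monitor and asks for consultation before discontinuation unless immediate action is warranted. Local-practice management would allow a commercial nucleos(t)ide if TAF were stopped. An investigator can also simply follow the stricter text. These points reduce the likely harm but do not reconcile the two instructions.

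**Conclusion.** The contradiction is real for one class of event: a drug-related Grade 4 clinical event judged not clinically significant. There 6.9.1 and the synopsis mandate a stop and 7.7.3 permits continuation. The first bullet's unnamed study drug is a separate ambiguity that, read literally, reaches TAF.

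The point is minor. Affected cases should be rare, and the documents give no Grade 4 clinical event rate for this combination. A reader might want to derive a limit from the regimens in Section 1.5 that report no related or no Grade 4 events. Those data come from other regimens and durations, and one of the selgantolimod denominators (93) includes placebo recipients, so no limit is claimed here.

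Nor should a reader infer an effect on the efficacy analysis population. Participants who stop treatment are to remain in follow-up, and the Full Analysis Set needs only enrollment and one dose. What can change is the treatment received and the count of discontinuations.

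The conclusion rests on the current text of 6.9.1, 7.7.3, Table 6 and the synopsis, and on the absence of a precedence clause in the text shown. It makes no claim about laboratory abnormalities.

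**What to change.** Two edits to Section 7.7.3:

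- Second bullet: delete *or clinical event*, so that the exception covers laboratory abnormalities only.
- First bullet: for Grade 4 clinical events, state that the treatment(s) considered related are permanently discontinued as in 6.9.1, with TAF continued unless it is itself considered related.

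Stops for unrelated Grade 4 clinical events then fall under the discretionary criteria already in 6.9.1. That section and the synopsis need no change. The cost is a wording amendment, with no new data, visits or analyses. What is given up is the automatic stop that the first bullet now suggests for unrelated events; the decision would rest on the investigator's causality judgment, which is harder when several drugs are given together, and on the discretionary criteria.
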